11.1. Handling of Participant Withdrawals or Termination

All data collection relating to a withdrawn or terminated participant, excluding safety data for participants that have received PD G 506 A, will cease at the time of withdrawal/termination. Clinical care in all withdrawn or terminated participants will continue as per standard of care.

In order to maintain the required number of study subjects, any participant that withdraws or is terminated prior to completion of the Week 2 visit will be replaced. Participants that withdraw or are terminated after the Week 2 visit but prior to the 1 year follow-up will not be replaced.

SBI-CIP 20-002 Rev: v1.8 A prospective multi-center clinical study evaluating the use of PD G 506 A and the Eagle V1.2 Imaging System for the visualization of carcinoma during breast conserving surgery	Page: 61 of 157
---	-----------------

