Only data from participants in Part B will be used for the analyses of primary and secondary efficacy. Data from all participants in both Part A and Part B will be used for the evaluation of safety.

In Part B of the study, participants will be randomized in a ratio of 1:6 (Arm 1 [SoC]: Arm 2 [PD G 506 A]).

The randomization will be stratified by breast cancer type (invasive carcinoma with or without in situ carcinoma vs. in situ carcinoma alone). This will ensure an approximate ratio of 1:6 within each type of breast cancer. Preoperative diagnosis based on diagnostic tissue sampling performed during screening (e.g. percutaneous core needle biopsy, fine-needle aspiration cytology) will be

SBI-CIP 20-002 Rev: v1.8 A prospective multi-center clinical study evaluating the use of PD G 506 A and the Eagle V1.2 Imaging System for the visualization of carcinoma during breast conserving surgery	Page: 46 of 157
---	-----------------

used for stratification. Permuted blocks will be used to construct the randomization schedule and the randomization will be implemented using an interactive web response system.

Data from the SoC arm (Arm 1) will not be used for statistical analysis of the primary and most secondary endpoints. The purpose of the SoC arm is to compare resected tissue weight, patient reported cosmetic outcomes, re-excision prior to initiation of adjuvant therapies, re-excision within 1-year of index BCS, and safety between study arms as well as to minimize bias introduced into the SoC procedure if the *surgeon* is aware that they have an opportunity to revise the margins further after SoC is complete. A 3-month, 6-month and 1-year follow-up will be performed to evaluate patient reported cosmetic outcomes as well as the rate of re-excision across both study arms. The 6-month and 1-year follow-up data will be collected as an extension phase to the study, meaning database lock and analysis of all other endpoints will be performed following the last patient's 3-month follow-up data is collected. Analysis of 6-month and 1-year data will occur after the last patients 1-year visit. The clinical study report will be appended to include the 6-month and 1-year data, when available.

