10.1.2.5. Preparation and Administration of the Placebo

Participant's randomized to Arm 1 will receive drinking water as the placebo. Calculate the administration volume, in mL, according to the following:

Administration Volume (mL) =
$$\frac{Patient\ Weight\ (kg) \times 20\ ml}{30\ kg}$$

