will affect the immediate management of the participant's condition. In this case, the investigator must notify the Sponsor's pharmacovigilance vendor, spmd (spmd will notify the Sponsor) within 24 hours after breaking the blind. The date and reason that the blind was broken must be recorded in the source documentation and electronic case report form (eCRF), as applicable.

For participants that are withdrawn or are terminated, the investigator may be unblinded to the treatment allocation following documentation of the participants withdrawal/termination.

If any member of the blinded research team (e.g. *surgeon*, *surgeon's assistant*, research nurse or pathologist) is inadvertently unblinded at any time other than as defined by the study protocol, data collection will continue as per protocol. The time that the blind was broken and individual that was unblinded will be noted in the eCRF.

In the event of a Quality Assurance audit, the auditor(s) will be allowed access to unblinded study treatment records at the site(s) to verify that randomization/dispensing has been done accurately.

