15.4.2. Safety Population

The safety population includes all subjects who are randomized (Arm 1 and Arm 2) and receive PD G 506 A (Arm 2 only); this population will be used for all safety analyses.

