15.8. Safety Analysis

The safety of the procedure and device will be assessed for both Arm 1 and Arm 2. The rates of procedure-related WHO grade 3-5 adverse events, drug-related WHO grade 3-5 adverse events, and device-related WHO grade 3-5 adverse events will be summarized descriptively by treatment arm. Additional summaries may be performed. Full details will be provided in the SAP.

16. Data Management

Data management will be performed according to the Data Management Plan to ensure the accuracy, quality and integrity of the data.

eCRFs will be used to capture study assessments and data. The study coordinator or other delegated study staff will enter data from source documents into the eCRFs. Training will be provided for the electronic data capture (EDC) system. All study staff using the EDC system must have the necessary education, training, and experience or any combination of these. The investigator will be responsible for documenting employee education, training, and previous experience that pertain to the EDC system for all site staff using the EDC system. The investigator must maintain adequate security of the EDC system, including documentation that all users have been trained and a list of authorized users. To ensure all data entries can be tracked, all personnel responsible for data entry

|--|

must obtain a unique user identification (user ID) and password before any data can be entered in the eCRFs. Authorized study staff will be assigned a unique user ID only after receiving training.

The investigator must make study data accessible to the site monitor, other authorized representatives of the sponsor, and the appropriate regulatory authority inspectors. The eCRF for each subject will be checked against source documents at the site by the site monitor, and a final copy of the eCRF will be signed by the investigator with an electronic signature. A copy of the final eCRFs will be provided to the investigator in PDF after study closure to be kept in the investigator's study files. See the Data Management Plan for additional details.

17. Deviation from the Clinical Investigation Plan

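### Section 11.1 continues safety data collection after withdrawal only for recipients of PD G 506 A, so placebo patients who leave between dosing and Week 2 have less complete adverse event capture than Arm 2

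*Combined protocol and SAP*

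**What the plan says.** **Withdrawal rule.** For anyone who leaves the study, Section 11.1 states: "All data collection relating to a withdrawn or terminated participant, excluding safety data for participants that have received PD G 506 A, will cease". Under Section 10.1.2.5, participants "randomized to Arm 1 will receive drinking water as the placebo".

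**Other sections on the same patients.** Section 13.3 has the investigator record events that start between consent and the Week 2 visit (Day 10-14), with no distinction by arm and no exception for withdrawal. New events after Week 2 are not recorded. Section 12.10 follows early-terminated participants for AEs to Week 2 if they left after administration of the investigational drug; it does not mention placebo.

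**Use of the data.** Section 8.1 lists among the purposes of Arm 1 a comparison of "re-excision within 1-year of index BCS, and safety between study arms". Section 15.8 says "The safety of the procedure and device will be assessed for both Arm 1 and Arm 2", and that the rates of procedure-, drug- and device-related grade 3-5 events "will be summarized descriptively by treatment arm". The safety population in Section 15.4.2 "includes all subjects who are randomized (Arm 1 and Arm 2) and receive PD G 506 A (Arm 2 only"), so every randomized Arm 1 patient counts.

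**Blinding.** Under Section 10.3 the surgeon and assistant are blinded until the standard-of-care (SoC) lumpectomy is complete. For participants who withdraw or are terminated, "the investigator may be unblinded to the treatment allocation following documentation of the participants withdrawal/termination".

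**The concern.** In a randomized, placebo-controlled safety comparison, AEs should be ascertained in the same way in both arms. Here the length of ascertainment after exit depends on the product received. A placebo patient who leaves early stays in the Arm 1 denominator, but events that start after exit cannot enter the numerator. A dosed Arm 2 patient who leaves at the same point is still followed. Arm 1 is the trial's only concurrent measure of the background rate of surgical complications, and it is small, so a few unrecorded events would show.

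There is also a lesser, operational point. The rule cannot be applied without knowing the arm. If a patient is terminated after dosing but before SoC is complete, the surgeon and assistant do not yet know it.

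**Working it through.** **1. Arm sizes (Section 15.2).** The inputs are a null of 1%, an expected rate of 3%, two-sided alpha 0.05 and 90% power. A one-sample Z test with the null variance gives n = [1.960·√(0.01·0.99) + 1.282·√(0.03·0.97)]² / 0.02² = 427.7, so 428 in Arm 2. Then 428 × 7/6 = 499.3, so 500 in total and 72 in Arm 1, and 500 × 1.05 = 525. The plan's figures reproduce. They are used here only for the arm sizes.

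**2. Who is treated differently under Section 11.1.**

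| Situation | Arm 1 | Arm 2 |
|---|---|---|
| Leaves before dosing | collection stops | collection stops |
| Leaves after dosing; event began before exit | recorded | recorded |
| Leaves after dosing but reachable; event begins after exit and by Week 2 | **not collected** | **collected** |
| Unreachable | not obtainable | not obtainable |
| Leaves after Week 2 | new events not recorded | new events not recorded |

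Only the third row differs. Section 13.3 would have those Arm 1 events recorded; Section 11.1 would not.

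**3. Number affected.** The documents give no rate of exit between dosing and Week 2. Assume d = 2-5%: 72 × 0.02 = 1.4 and 72 × 0.05 = 3.6, so about 1 to 4 Arm 1 patients. With 75 in Arm 1 (525/7) the figures are 1.5 and 3.75. Counting at most one event per patient, one missed event is 1/72 = 1.4 points (1/75 = 1.3).

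**4. Size of the bias.** Let the true rate r be the same in both arms. Let withdrawn patients have k times that rate, and let a share f of their events begin after exit.

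Observed Arm 1 rate = r − d·k·r·f; observed Arm 2 rate = r.

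All values below are assumptions.

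| r | d | k | f | Arm 1 understated by (points) | Events lost of 72 | Apparent Arm 2/Arm 1 ratio |
|---|---|---|---|---|---|---|
| 2% | 2% | 1 | 0.5 | 0.02 | 0.01 | 1.01 |
| 5% | 5% | 3 | 0.5 | 0.38 | 0.27 | 1.08 |
| 10% | 5% | 5 | 1 | 2.5 | 1.8 | 1.33 |

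The first and last rows bound the grid r = 2-10%, d = 2-5%, k = 1-5, f = 0.5-1. The last row supposes that half of the withdrawn patients have an event (5 × 10%) and that all of those events begin after exit.

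**5. Against sampling error.** The standard error of the between-arm difference, √[r(1−r)(1/72 + 1/428)], is 1.8, 2.8 and 3.8 points at r = 2%, 5% and 10%. The bias is below one standard error throughout the grid.

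**The case against.** The best case on the other side is that this is a wording conflict with little consequence. Several parts of it stand.

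- **Window.** Only reachable patients who leave between a single dose and about two weeks later are affected. The only 5% in the plan is loss to follow-up, and Section 11.2 classes unreachable patients as withdrawn; their later events are largely unobtainable in either arm.
- **Endpoints.** Arm 1 drinks water, and under Section 12.4.3 the device images only its excised specimens. Drug- or device-related events are hardly possible there, which leaves mainly the procedure-related rate.
- **Analysis.** It is descriptive, and the primary endpoint uses Arm 2 only.
- **Section 12.10 may already cover placebo.** The protocol sometimes uses investigational drug for blinded product generally, as in the sunscreen instructions for all participants (Sections 10.5 and 12.4.5). Elsewhere it names drug or placebo when it means both (Sections 10.3 and 12.4.1). The section can be read either way, so it does not settle the matter.

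A reader might also infer four stronger things that the documents do not support:

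- *Every Arm 2 withdrawal keeps safety follow-up.* Those who leave before dosing do not, and some exits listed in Section 11, such as surgery moved to a non-study site, can fall before dosing.
- *The events that cause patients to leave are lost.* They precede exit and are recorded in both arms. What is lost is what begins, or worsens, afterwards.
- *The rule breaks the blind.* The surgeon knows the arm once SoC is complete, and Section 10.3 permits unblinding the investigator after a documented withdrawal. Withdrawn participants supply no further questionnaire data that could be biased.
- *The rule could hide a harm of PD G 506 A.* The bias runs the other way and makes the drug look relatively worse.

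None of this justifies a different rule by arm, and nothing in the protocol clearly restores follow-up for withdrawn placebo patients.

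**Conclusion.** The point holds as a limited defect. Followed as written, Section 11.1 gives unequal AE capture by arm for patients who leave between dosing and Week 2, and it contradicts Section 13.3. The direction is certain: the Arm 1 rate can only be understated. The size is not known, because the documents give neither a withdrawal rate nor an AE rate for the window. On the stated assumptions it runs from negligible to about 2.5 points, and the upper end needs assumptions that all lean the same way. It is probably small. It affects a descriptive comparison and no hypothesis test. It is still worth correcting, because that comparison is one of the reasons for having Arm 1. The dependence on the assignment is secondary: the protocol allows for it, but a common rule would make it unnecessary.

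**What to change.** State in Section 11.1 that safety data collection continues to the Week 2 visit for every participant who received PD G 506 A or placebo, unless the participant withdraws consent for safety follow-up. Name both products in Section 12.10, and reconcile Sections 11.1, 12.10 and 13.3 so that they give one rule.

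The differential loss then falls to zero, and the site no longer needs the assignment to apply the rule. Sample size, endpoints and treatment are unchanged. The cost is a short wording amendment and AE follow-up on a handful of placebo patients.

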11.2. Loss to Follow Up

A participant will be considered lost to follow-up if they fail to return for scheduled visits and are unable to be contacted by the study site.

The following actions must be taken if a participant fails to return to the clinic for a required study visit:

[figure not shown]
- The site must attempt to contact the participant and reschedule the missed visit as soon as
 possible and counsel the participant on the importance of maintaining the assigned visit
 schedule and ascertain whether or not the participant wishes to and/or should continue in
 the study.
- Before a participant is deemed lost to follow up, the investigator or designee must make
 every effort to regain contact with the participant (where possible, 3 telephone calls and, if
 necessary, a certified letter to the participant's last known mailing address or local
 equivalent methods). These contact attempts should be documented in the participant's
 medical record.
- Should the participant continue to be unreachable, they will be considered to have withdrawn from the study with a primary reason of lost to follow-up.

For the purposes of the 6-month and 1-year follow-up, any participant who may have died within 6-months or 1 year of their index BCS procedure or for whom follow-up data cannot be retrieved (either through medical record review and/or telephone contact with the participant), will be considered lost to follow-up for the extension phase of the study. Data from participants that are lost to follow-up for the extension phase will still be used for analysis of all endpoints that are based upon data collected through the Month 3 visit.

12. Study Procedures and Schedule

- Immediate safety concerns should be discussed with spmd immediately upon occurrence or awareness to determine if the participant should continue or discontinue study treatment.
- Adherence to the study design requirements, including those specified in the Schedule of Activities, is essential and required for study conduct.
- All screening evaluations must be completed and reviewed to confirm that potential participants meet all eligibility criteria. The investigator will maintain a screening log to record details of all participants screened and to confirm eligibility or record reasons for screening failure, as applicable.
- Procedures conducted as part of the participant's routine clinical management (e.g. diagnostic imaging and histopathology, bloodwork) and obtained before signing of the ICF may be utilized for screening or baseline purposes provided the procedures met the protocol-specified criteria and were performed within the time frame defined in the Schedule of Activities.

12.1. Schedule of Activities

*baseline bloodwork must be performed ≤ 7 days prior to the surgical procedure

Figure 12.1: Schematic of Study Visits and Procedures through Week 2 Visit

SBI-CIP Rev: 50	prospective multi-center clinical study evaluating the use of PD G 06 A and the Eagle V1.2 Imaging System for the visualization of arcinoma during breast conserving surgery	Page: 63 of 157
-----------------	---	-----------------

Table 5.1: Schedule of Study Assessments and Procedures.

List of study specific assessments and procedures to be performed at each study visit.

List of study specific a					 			3-month	6-month	1 Year
	Baseline		D	ay 1		Day 2	Week 2	Follow-up ^r	Follow-up	Follow-up
				··· ·				(In-Pers	on Visit not R	equired)
Study Assessment or Procedure	≤90 to Day 0 before procedure	Before PD G 506 A dosing & surgical procedure	PD G 506 A dosing	Surgical procedure	After PD G 506 A dosing & surgical procedure	24 – 48 hours post- procedure ⁿ	10 days – 14 days post- procedure (Last In-Person Study Visit)	80 – 90 days post- procedure	168 – 182 days post- procedure	365 – 379 days post- procedure
Informed consent	X									
Eligibility criteria	X	X								
Demographics and Medical history	X									
Randomization	X									
Adverse event evaluations	X	X	X	X	Xº	X	Xp			
Concurrent meds	X	X				X	X			
Physical Examination ^a	Xb	Xb					X			
Vital signs		X	X		X					
CBC, AST, ALT, TBL, creatinine c, d, e	X						X			
IMAGING (at least one of: mammography, ultrasound, MRI) ^{f, g}	X									
Diagnostic tissue sample collection (e.g. PCNB, FNAC) ^{g, h}	X									
Breast-Q questionnaire	X						X	X	X	X
Pregnancy Testi	\mathbf{X}^{j}	X^k								
PD G 506 A / placebo l, m			X							
Sunscreen application and					X					
sun protection instructions					Λ					
SoC lumpectomy				X						
Eagle V1.2 Imaging				X						
System assessment										
FL-guided resection				X						
Resected tissue weight					X					
Pathology assessment							X			

SBI-CIP 20-002	Rev: v1.8	A prospective multi-center clinical study evaluating the use of PD G 506 A and the Eagle V1.2 Imaging System for the visualization of carcinoma during breast conserving surgery	Page: 64 of 157
-----------------------	--------------	--	-----------------

	Baseline		Da	ay 1		Day 2	Week 2	3-month Follow-up ^r (In-Perso	6-month Follow-up on Visit not F	1 Year Follow-up Required)
Study Assessment or Procedure	≤90 to Day 0 before procedure	Before PD G 506 A dosing & surgical procedure	PD G 506 A dosing	Surgical procedure	After PD G 506 A dosing & surgical procedure	24 – 48 hours post- procedure ⁿ	10 days – 14 days post- procedure (Last In-Person Study Visit)	80 – 90 days post- procedure	168 – 182 days post- procedure	365 – 379 days post- procedure
(report) of surgical specimens										
Medical chart review - additional procedures ^q								X	X	X

- a. Physical exam includes (at a minimum): height (baseline visit only), weight, vitals (heart rate, blood pressure), auditory assessment of heart and lungs, assessment of skin, eyes, abdomen and lower extremities, assessment of any phototoxic reactions (Day 1, Day 2 and Week 2 visit only).
- b. An abbreviated physical exam (including weight, heart rate and blood pressure) may be performed on Day 1 prior to dosing if a complete physical examine (as described in (a)) has been performed no more than 7 days prior to surgery.
- c. CBC=complete blood count, AST=aspartate aminotransferase, ALT=alanine transaminase, TBL= Total bilirubin level
- d. Phosphorus, uric acid, creatinine kinase, & amylase will be added as clinically necessary/indicated.
- e. Baseline must be performed no more than 7 days prior to surgery
- f. Type of diagnostic imaging test dependent on site SoC
- g. May be performed up to 90 days prior to surgery
- h. PCNB=percutaneous core needle biopsy, FNAC=fine-needle aspiration cytology
- i. Pregnancy test for women of childbearing potential performed one time prior to surgery either within 7 days prior to surgery or the day of surgery prior to dosing
- j. If pregnancy test is performed within 7 days prior to surgery a blood pregnancy test must be performed
- k. If pregnancy test is performed on the day of surgery prior to dosing either a urine or blood pregnancy test may be performed
- PD G 506 A to be dosed 3 hours (target range: 2 hours 4 hours) prior to anesthesia
- m. PD G 506 A is dosed as 20 mg/kg BW. Oral administration is one-time only and based on actual body weight, measured ≤ 7 days prior to administration of the study drug
- n. For patients that are discharged on Day 1, Day 2 AE and concurrent medication evaluation will be performed via telephone questionnaire
- o. Clinical laboratory tests as required to investigate (S)AEs (e.g. blood work)
- p. Any unresolved AEs present at Week 2 visit will be followed for an additional 7 days. Any unresolved SAEs will be followed for an additional 30 days. Patients with elevated liver enzymes will be followed until levels return to baseline.
- q. Medical chart reviewed to identify additional therapies related to the breast cancer diagnosis received since the Week 2 visit and within 1 year following Day 1 (e.g. additional surgeries, chemotherapy, radiation therapy, endocrine therapy, immunotherapy). In the event the patient is no longer under the care of the study investigator, the patient will be contacted via telephone.
- r. 3-month follow-up data must be collected 80-90 days post-procedure or within 7 days prior to commencement of radiation therapy, whichever occurs first.
- s. Includes assessment of neurological AEs (neurological AEs observed in the clinical trials of ALA HCl used for the visualization of glioma during surgical resection may be attributable to the greater amount of tissue resected in patients in the ALA arm as compared to control and are not expected to occur in breast cancer patients; nevertheless investigators must evaluate potential neurological AEs at each AE assessment time point)

SBI-CIP 20-002	Rev: v1.8	A prospective multi-center clinical study evaluating the use of PD G 506 A and the Eagle V1.2 Imaging System for the visualization of carcinoma during breast conserving surgery	Page: 65 of 157
-----------------------	--------------	--	-----------------

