6.2.1. Previous clinical trials using ALA HCl

No major side effects are anticipated from the consumption of ALA HCl (based on previous studies³³). A Phase I study involving 21 healthy male subjects compared the absolute bioavailability of oral (20 mg/kg BW) relative to i.v. (2 mg/kg BW) ALA HCl administration and evaluated the duration of photosensitization of the skin by observing the minimal erythemal dose and corresponding PpIX plasma concentrations after oral treatment. Just 1 adverse event (AE) occurred in 1 subject 2.02 hours after oral administration. The symptom was mild nausea, assessed as probably drug related. The AE resolved without any action taken after 3 hours. There were no effects of the ALA HCl on laboratory values of clinical chemistry, hematology, and urinalysis; vital signs; electrocardiogram (ECG) parameters; or physical findings. Overall, both oral and i.v. formulations were assessed as safe and tolerable.

The administration of low (< 60 mg/kg BW) doses of ALA has no known long-term risks and is associated with minimal side effects³⁸. In the case of 139 patients given 20 mg/kg orally for contrast in malignant glioma³³ a toxicological safety analysis noted no concerns. Oral doses of 40 mg/kg³⁴ were also well tolerated, with transient minor side effects (facial erythema, peri-nasal swelling) dissipating within 72 hours of the applied dose. The same study also reported 5 patients who received doses as high as 60 mg/kg, which increased the intensity (but not the duration) of these side effects and was also associated with nausea in 3 of the 5 patients.

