12.5. Day 2 Follow-up (24 hours +24 hours post-surgery)

Between 24 – 48 hours after the surgery the participant will be contacted via telephone and asked about their adherence to the sun protection instructions, any self-reported adverse events and concomitant medications.

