12.7. Week 2 Visit (Day 10 – 14)

Clinical usefulness and diagnostic performance endpoint data will be collected at the participant's post-operative surgical follow-up visit.

At this visit, the participant will complete the post-operative Breast Conserving Therapy Module of the Breast-Q survey. To minimize the potential impact of timing of administration of the Breast-Q survey post-op questionnaire, all patients will complete the 2-week post-op questionnaire before they have met with their *surgeon* to discuss their surgical pathology report.

The participant's surgical pathology report will be available at this time. Endpoint data will be retrieved from the participant's surgical pathology report and the study-specific Pathology Data Collection Tool. Additional data related to the final pathological tumor staging, pathological features/characteristics and nodal involvement will be retrieved from the participant's surgical pathology report and recorded in the eCRF.

The *surgeon* will question the patient about any patient-reported Aes and use of concomitant medications as well as assess and record any ongoing adverse events in the participant's medical record and eCRF.

Blood work (CBC, AST, ALT, TBL, creatinine) will be performed at this visit. If liver enzymes are elevated from baseline (and deemed clinically significant according to the **Table 12.2** below), the patient will be followed until such time that liver enzyme levels return to baseline. Physical examination must include assessment of any phototoxicity reactions and any observed phototoxicity reactions will be followed until resolution.

Table 12.2: Criteria for clinical significant liver enzyme elevation

	SBI-CIP 20-002	Rev: v1.8	A prospective multi-center clinical study evaluating the use of PD G 506 A and the Eagle V1.2 Imaging System for the visualization of carcinoma during breast conserving surgery	Page: 77 of 157
--	-----------------------	--------------	--	-----------------

Criteria	CTCAE v5.0 Grade 2 (moderate) as criterium to judge if elevation of liver enzymes should be deemed clinically significant
Bilirubin: above upper limit of normal	Bilirubin:
	> 1.5 – 3.0x institutional* ULN if baseline normal
	> 1.5 – 3.0x baseline if baseline abnormal
AST: > 2.5x institutional ULN	AST:
	> 3.0 – 5.0x institutional* ULN if baseline normal
	> 3.0 – 5.0x baseline if baseline abnormal
ALT: > 2.5x institutional ULN	ALT:
	> 3.0 – 5.0x institutional* ULN if baseline normal

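### Footnote a of the Schedule of Activities calls for a Day 2 assessment of phototoxic reactions that the examination row does not schedule and Section 12.5 does not name, so the first scheduled post-dose physical examination is at Days 10–14

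*Combined protocol and SAP*

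**What the plan says.** Five places in the protocol govern what is assessed on Day 2 and how.

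- **Section 12.1, footnote a.** The content of the physical examination includes "assessment of any phototoxic reactions (Day 1, Day 2 and Week 2 visit only").
- **Section 12.1, the row "Physical Examination".** It carries footnote a and is marked at baseline, on Day 1 before dosing, and at Week 2. The Day 1 cells for dosing, surgery and the period afterwards are empty, and so is Day 2. Footnote b adds that an abbreviated version (weight, heart rate, blood pressure) "may be performed on Day 1 prior to dosing" if a complete examination was done within the preceding 7 days.
- **Section 12.5.** Between 24 and 48 "hours after the surgery the participant will be contacted via telephone" and asked about "adherence to the sun protection instructions, any self-reported adverse events and concomitant medications".
- **Section 12.1, footnote n.** The telephone questionnaire is provided for patients who are discharged on Day 1.
- **Appendix 2, Day 2 follow-up step.** The telephone is optional, for a participant who has been discharged.

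For Week 2, Section 12.7 is explicit: "Physical examination must include assessment of any phototoxicity reactions", and anything observed is followed until it resolves.

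**The concern.** Sections 6.2.6, 10.4, 10.6 and 10.7 all set precautions against photosensitivity, mostly for 48 hours after dosing. Footnote a appears to be the plan's provision for checking in that period whether a reaction has occurred. If the row and Section 12.5 do not carry it out, sites will handle Day 2 differently. Some may examine or ask specifically because of footnote a, and others will make a general call because of Section 12.5. Adverse-event summaries would then mix two levels of ascertainment, with mild, short-lived reactions after discharge the most exposed to loss.

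The comparison between arms has a further weakness. Section 10.3 unblinds the surgeon once standard-of-care resection is complete, and Section 12.7 has the surgeon question the patient at Week 2. A general question leaves the depth of probing to someone who knows the arm.

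**Working it through.** The plan states no figure on this point to reproduce. The check is a cell-by-cell reading, followed by simple arithmetic on the time windows.

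**1. Footnote a against its own row.**

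| Day named in footnote a | Examination marked? | After dosing? |
|---|---|---|
| Day 1 | Yes, before dosing only; may be abbreviated under footnote b | No |
| Day 2 | No | – |
| Week 2 | Yes | Yes |

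Scheduled physical examinations after dosing and before Week 2: 0. An examination before dosing cannot show a reaction to the study drug.

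**2. Mode of the Day 2 contact.** Section 12.5 gives a telephone call with no exception. Footnote n gives the telephone for patients discharged on Day 1. Appendix 2 permits it once the patient has been discharged. For a patient still in hospital on Day 2, Section 12.5 gives a call, while the other two leave room for an in-person contact. None of the three refers to the examination in footnote a.

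**3. Timing of the contacts.**
- Week 2: 10 × 24 = 240 hours to 14 × 24 = 336 hours after surgery.
- Day 2: 24–48 hours after surgery. Dosing is 2–4 hours before anesthesia, so the contact falls from 24 + 2 = 26 to 48 + 4 = 52 hours after dosing, plus the length of surgery, which the protocol does not give.
- The precaution period in Section 10.7 is at least 48 hours after dosing. Counting from surgery, which understates the time since dosing, the earliest Week 2 visit is 240 − 48 = 192 hours (8 days) later.
- Section 6.2.1 gives one duration, from a cited study at 40 mg/kg: "transient minor side effects (facial erythema, peri-nasal swelling) dissipating within 72 hours of the applied dose". The earliest Week 2 visit is at least 240 − 72 = 168 hours (7 days) beyond it. The Day 2 contact falls inside 72 hours provided surgery lasts less than 72 − 52 = 20 hours.

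Of the two scheduled contacts after discharge and up to Week 2, Day 2 is therefore the one that falls while a short-lived reaction would probably still be present.

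**4. Other capture routes.** The adverse-event row is marked on Day 1 after dosing, on Day 2 and at Week 2. Section 12.4.5 requires an adverse-event check before discharge. Section 13.3 has the investigator ask at each visit about events since the previous one. These routes cover phototoxic reactions as adverse events in general, without naming them.

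**The case against.** The strongest reply is that this is mostly a footnote error and that general adverse-event collection already covers the gap. Much of that stands, and it rules out several stronger readings.

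- A reader might infer that the Day 2 contact leaves phototoxic reactions out. The documents do not support this. The call covers any self-reported adverse event, and it follows patient instructions on phototoxicity and a question on sun-protection adherence. The questionnaire mentioned in footnote n is not among the documents, so its items cannot be judged. What can be said is that Section 12.5 does not name these reactions.
- A reader might infer that skin is first looked at when any reaction is already gone. That is too strong. Adverse events are evaluated before discharge, an inpatient may be seen on Day 2, and Section 12.7 foresees reactions still present at Week 2. The 72-hour figure concerns minor effects at 40 mg/kg, not the trial's 20 mg/kg, and Section 6.2.1 does not label them phototoxic.
- A reader might infer that a planned phototoxicity rate is biased downward. No such rate is an endpoint. Sections 7.4 and 15.8 specify related events of grade 3–5, which patients are more likely to report.
- A reader might rank phototoxicity as the drug's leading hazard. The protocol does not; Section 6.2.2 refers drug effects to the Investigator's Brochure.

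The reply does not remove the contradiction. General collection is not the specific assessment that footnote a calls for. The protocol also accepts elsewhere that naming an event helps: Section 13.3 asks for neurological events at every adverse-event time point, although footnote s says they are not expected in these patients.

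**Conclusion.** The inconsistency is real and lies on the face of the text. Footnote a names three days. Only one of them, Week 2, has a scheduled physical examination after dosing, and it falls at Days 10–14. Section 12.5, footnote n and Appendix 2 disagree on the mode of the Day 2 contact, and Section 12.5 does not name the assessment that footnote a places on that day.

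The consequence is limited. Transient reactions between discharge and Week 2 are captured mainly by self-report to a general question and could be under-ascertained. The number that might be missed cannot be estimated from the documents. The primary and secondary efficacy endpoints are untouched, and the grade 3–5 safety endpoints are less likely to be affected than summaries of milder events.

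This rests on two assumptions: that the row's columns are read correctly from the extracted table, and that the Day 2 questionnaire follows the content given in Section 12.5. If the questionnaire already names phototoxic reactions, the remaining point is the inconsistency alone.

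**What to change.** 1. Reconcile footnote a, the physical examination row, footnote n, Section 12.5 and Appendix 2 so that they agree on what is assessed on Day 2 and by what mode. The choice of mode is the sponsor's.
2. Whatever the mode, name phototoxic reactions as a specific item of the Day 2 contact. Use fixed questions (for example redness, swelling, burning or blistering of exposed skin, yes or no, with onset), asked in the same words in both arms.
3. At Week 2, keep the existing inquiry about events since the last visit and have it name phototoxic reactions, alongside the examination for current signs that Section 12.7 already requires.

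The cost is a few questions on a contact that already takes place, corrections to the schedule and its footnotes, and possibly more mild events recorded. Because patients are blinded and the wording is fixed, any extra mild events can be compared like for like with the placebo arm.
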